6.0 Statistical Analysis Plan

We will use descriptive statistics to characterize the study participants and survey data. We will use a one sample t-test to compare the mean SUS score at T1 to the threshold score of 71 indicative of "good" usability. To assess whether there was a significant improvement in the continuous secondary cognitive/behavioral outcomes from baseline to end of study (T₀ to T₁), we will perform two-sided paired t-tests on the pairwise differences. If any of the distributions of pairwise differences suggest asymmetry or nonnormality, the non-parametric Wilcoxon signed-rank test will be performed in lieu of paired t-tests. We will use the McNemar's test for to compare paired proportions. Our primary outcome will be System Usability Scale (SUS) score at the end of the study period (T1).

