2.0 Rationale and Specific Aims

To assess usage patterns, user experience, and to uncover errors in functionality prior to larger interventional trials, we will conduct a longitudinal usability study MDC-m. The study will utilize questionnaires to quantify participants' perceptions and responses to the MDC-m and semi-structured interviews to comprehensively assess users' experience, barriers to use, and reasons for non-use or discontinued use. Combining qualitative and quantitative assessments of usability identifies more usability concerns than quantitative (e.g., questionnaires) assessments alone. Each participant will have access to the MDC-m for 1 month from the time of enrollment. This duration allows sufficient time for participants to become familiar with MDC-m and determine if and how to use MDC-m in the management of their diabetes.

In the current study, we aim to: (1) assess the feasibility of the intervention and (2) the usability of the MDC-m over time among a diverse group of patients with type 2 diabetes mellitus (T2DM).

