5.0 Study Procedures

Setting. The Vanderbilt Adult Primary Care (VAPC) clinics are located throughout the greater Nashville, TN area. An EHR (Epic Systems Corp.) stores all clinical data and patients receive access to their clinical data via an integrated and highly-adopted patient web portal, My Health at Vanderbilt (MHAV), that is accessible on desktops and via a native mobile app for iOS and Android mobile operating systems.

Participants and Recruitment. Potential participants will be identified automatically using VUMC's *Subject Locator* to query the EHR for patients with upcoming clinic appointments who meet the discrete inclusion and exclusion criteria. In addition, VUMC population health and quality improvement initiatives have created a report that identifies established patients with diabetes who receive care at the primary care clinics participating in the study. These patients are the target population for study (i.e., Vanderbilt primary care patients with diabetes) and as such these patients are potentially eligible to participate in the study. With permission of the clinic director, potentially eligible patients, will be mailed a recruitment letter describing the study and providing contact information for IRB approved study personnel. If after a receiving the letter, a patient is interested in the study, the patient may contact study personnel to learn more and consider participating in the study. The recruitment letter will include a QR code and URL link to the eligibility screener in Research Electronic Data Capture (REDCap). Participants whose REDCap screener indicates they are eligible can advance to the REDCap ICD. Participants will complete an electronic consent form and enroll online via REDCap. Our target enrollment is 65 participants. In accordance with best practices and to reflect a range of patient experience with diabetes and groups with distinct usability needs, we will aim to recruit a study sample with at least 25% representation of each of the following characteristics: (a) limited health literacy and (b) age 65 or over. Some participants may have one or more of these characteristics.

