Data Collection and Outcome Measures. Study participants will complete questionnaires electronically via email using REDCap at two time points: enrollment (T_0) and end of study (T_1). Participants will complete an enrollment questionnaire (T_0) including basic sociodemographic questions and validated measures of health literacy and eHealth literacy.

The primary outcome measures (**Table 1**) will be: (a) ease of use and satisfaction as assessed by the System Usability Scale at T_1 , (b) system usage data of MDC-m at T_1 , (c) user experience as assessed by end of study questionnaire and semi-structured interviews at T_1 . In addition, we will assess pre/post change in the following secondary cognitive and behavioral outcomes (Table 1) to estimate effect size and standard deviations for power analyses necessary to plan subsequent randomized controlled trials.

Table 1. Outcome Measures

Primary Outcomes	Measures	Variable Type	How Collected	Time Point
Usability	System Usability Scale	Continuous	Questionnaire	T_1
System usage data	MDC-m visits Duration of MDC-m visits	Continuous and categorical	Self-report	T_1
User experience	Assess participants' perspectives on content, layout, acceptance, and particular features and functionality	Categorical, Qualitative	Questionnaire, Interviews	T_1
Secondary Cognitive/Behavioral Outcomes				
Diabetes knowledge	Short Diabetes Knowledge Instrument (SDKI)	Continuous	Questionnaire	T_0 and T_1
Diet adherence	Summary of Diabetes Self-Care Activities (SDSCA) – General Diet Subscale Summary of Diabetes Self-Care Activities (SDSCA) – Specific Diet Subscale	Continuous	Questionnaire	T_0 and T_1
Exercise adherence	SDSCA – Exercise Subscale	Continuous	Questionnaire	T_0 and T_1
Medication adherence	Adherence to Refills and Medications Scale	Continuous	Questionnaire	T_0 and T_1
Glucose self-monitoring adherence	SDSCA – Self-monitoring of Blood Glucose Subscale	Continuous	Questionnaire	T_0 and T_1
Medication adherence	Adherence to Refills and Medications Scale (ARMS)	Continuous	Questionnaire	T_0 and T_1
Diabetes self-efficacy	Perceived Diabetes Self-Management Scale (PDSMS)	Continuous	Questionnaire	T_0 and T_1
Diabetes distress	Problem Areas in Diabetes Scale (PAID)-5	Continuous	Questionnaire	T_0 and T_1
Knowledge of Diabetes Measures	Unique study specific items to assess participants' knowledge of measures of diabetes health status	Categorical	Questionnaire	T_0 and T_1

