Diabetes Attitudes	Unique study specific items to assess participants' attitudes toward social and goal-based comparison information regarding their diabetes health status	Categorical	Questionnaire	T_0 and T_1

Diabetes Readiness for Change	Four items assessment resources to assess stage of change based on the Transtheoretical Model (TTM) of behavior change. It includes questions on physical activity, medication management, glucose self-monitoring, and diet.	Categorical	Questionnaire	T ₀ and T ₁
-------------------------------	---	-------------	---------------	-----------------------------------

Based on pilot testing, we estimate time to completion for questionnaires to be 20 minutes at T₀ and 25 minutes at T₁. Participants will be compensated \$40 for completing the enrollment questionnaire, \$35 for completing the study end questionnaire, and \$5 for first 10 minutes of MDC-m use during which participants will be encouraged to familiarize themselves with the full functionality of the MDC-m.

At the conclusion of their one month of MDC-m access, we will conduct one-on-one, semi-structured interviews with a subsample of at least 10 participants including at least two participants from each of the purposively sampled groups (i.e., participants with limited health literacy and age 65 or over). This methodology is most appropriate for in-depth assessment of patients' perceptions and reactions regarding a proposed intervention. Interviews are preferred over focus groups for understanding usability because focus groups can amplify bias and individual opinions. Interviews will take place by phone or via Zoom within two weeks of participants concluding their one month of MDC-m access and will last approximately 30-40 minutes. Participant MDC-m access will be available during the interview to allow participants to recall and/or reference particular concerns or perceptions of usability. A trained interviewer will use a semi-structured interview guide to facilitate the interview and elicit in-depth understanding of participants' perceptions and experiences with specific MDC-m functionality as well as barriers to use, and reasons for non-use or discontinued use. Additional participants will be enrolled until saturation is reached. Saturation will be defined as no new usability concerns raised in the preceding two interviews and typically occurs between 10 and 30 interviews. Participants will be compensated an additional \$40 for the interview.

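### Does the plan need a SUS estimate for the limited-health-literacy and 65-and-over groups alongside the overall test against 71?

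*Combined protocol and SAP*

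**What the plan says.** Section 6.0 names the System Usability Scale (SUS) score at T1 as the primary outcome and gives it one inferential analysis: "We will use a one sample t-test to compare the mean SUS score at T1 to the threshold score of 71". It mentions no subgroup, age band or health-literacy level. It also has a general sentence: "We will use descriptive statistics to characterize the study participants and survey data".

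Section 5.0 (Participants and Recruitment) sets a target enrolment of 65 and states: "we will aim to recruit a study sample with at least 25% representation of each of the following characteristics", namely limited health literacy and age 65 or over. The reason given is "to reflect a range of patient experience with diabetes and groups with distinct usability needs". Overlap is allowed: "Some participants may have one or more of these characteristics".

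The interview subsample in Section 5.0 is at least 10 people and must include "at least two participants from each of the purposively sampled groups", with recruitment continuing to saturation. The usability aim in Section 2.0 is to assess "the usability of the MDC-m over time among a diverse group of patients" with type 2 diabetes.

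**The concern.** The plan says these two groups may have distinct usability needs and shapes recruitment around that, yet its main usability measure is planned only as one overall mean. An overall mean above 71 is arithmetically compatible with a group mean below 71, and the specified test would not show it. If that happened, the tool could go forward to larger trials rated as having good usability while falling short for older patients or those with limited health literacy. The data for a breakdown are to hand: age is needed for the recruitment target, and the enrolment questionnaire includes "validated measures of health literacy and eHealth literacy".

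**Working it through.** **What the plan commits to.** The 25% figures are recruitment aims about sample composition. Section 2.0 asks about usability in one diverse group, and the one-sample test in Section 6.0 estimates the mean of that group. No section states a group hypothesis or promises a group estimate, so no commitment is left without an analysis. The targets also make the overall mean respond to these groups: with 17 of 65, each point that a group loses lowers the overall mean by 17/65 = 0.26 points.

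**Inputs.** From the plan: N = 65, 25% per group, threshold 71. The plan gives no SUS mean, SD or sample-size calculation, so there is no figure to reproduce. Assumed here: within-group SD s = 12, 15 or 20; group means of 62 or 66; two-sided 5% level; all 65 complete T1.

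**Group size.** 0.25 × 65 = 16.25, so at least 17 per group. With overlap allowed, that minimum is 17 to 34 distinct people.

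**Overall mean exactly 71, group of 17.** The other 48 must average:
- group at 62: (71 × 65 − 17 × 62)/48 = 3561/48 = 74.2
- group at 66: (71 × 65 − 17 × 66)/48 = 3493/48 = 72.8

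**Overall result significantly above 71.** Let n1 and m1 be the size and mean of the group, n2 and m2 those of the others, and m the overall mean. The total SD is √{[(n1−1)s² + (n2−1)s² + n1(m1−m)² + n2(m2−m)²]/64}. Solve (m − 71)/(SD/√65) = t(0.975, 64) for m2.

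| Group | m2 at s = 12 / 15 / 20 | Gap m2 − m1 | Gap ÷ s |
|---|---|---|---|
| n = 17, mean 62 | 78.9 / 79.8 / 81.5 | 16.9 / 17.8 / 19.5 | 1.4 / 1.2 / 1.0 |
| n = 17, mean 66 | 77.1 / 78.1 / 79.7 | 11.1 / 12.1 / 13.7 | 0.9 / 0.8 / 0.7 |
| n = 26, mean 66 | 80.0 / 81.2 / 83.3 | 14.0 / 15.2 / 17.3 | 1.2 / 1.0 / 0.9 |

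Check of one cell (n = 17, mean 66, s = 15): m = (17 × 66 + 48 × 78.08)/65 = 74.92; SD = 15.81; SE = 15.81/√65 = 1.96; (74.92 − 71)/1.96 = 2.00, which is t(0.975, 64).

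For a significant result to hide a low group, the gap must therefore be about 0.7 to 1.4 within-group SDs. Nothing in the documents points to a gap of that size. A larger group makes masking harder.

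**What a group estimate would add.** The 95% CI half-width is t(0.975, n−1) × s/√n.
- n = 17: 6.2, 7.7 and 10.3 points for s = 12, 15 and 20.
- n = 13 (if some do not complete T1): 9.1 points for s = 15 and 12.1 for s = 20.

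By the noncentral t distribution, the n = 17 interval lies wholly below 71 with probability 0.83, 0.64 and 0.41 if the true group mean is 62, but only 0.37, 0.25 and 0.16 if it is 66. For a modest shortfall the estimate would usually be inconclusive.

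**The case for a change.** The strongest case for the concern is that the protocol itself expects these groups to differ in usability. Naming a breakdown in advance would commit the sponsor to report it whatever it showed, and it would cost two or three sentences and no new data. The general sentence on descriptive statistics permits a breakdown but requires none. Two interviewees per group is a low floor and gives no SUS estimate. Section 2.0 itself favours combining qualitative and quantitative assessment. An overall mean that is merely above 71, without significance, needs far smaller gaps (others above 72.8 with the group at 66).

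All of that is accurate, and a descriptive table by age and health literacy would be reasonable. It does not show an error. The specified test is valid for the stated aim, nothing in the plan contradicts it, and adding the table would change no planned result. The interviews, which ask about barriers to use and reasons for non-use, are the part of the design best placed to find a usability problem specific to one group. The health-literacy half of the table would also need an instrument and cut-off that the documents do not name.

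**Conclusion.** The concern does not hold. The single test of mean SUS against 71 is a sound answer to the aim in Section 2.0. The recruitment targets broaden the sample without creating a duty to estimate SUS by group, and the interviews must include both groups. The facts behind the concern are right, since no group-level SUS estimate is planned, but this is a reporting preference. Its practical weight is small: a significant overall result that hid a group mean of 62 or 66 would need a gap of about 11 to 19 points at n = 17, and an interval from 17 people would lie wholly below 71 only 16% to 37% of the time at a true mean of 66. These figures rest on assumed SUS means, SDs of 12 to 20, recruitment targets met and full completion at T1. The conclusion itself rests on what the plan sets out to estimate and does not depend on those assumptions.

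### Does the SAP need a stated cut or an ordinal paired test for the four stage-of-change items?

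*Combined protocol and SAP*

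**What the plan says.** Section 6.0 has three parts that bear on this point.

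- Description: "We will use descriptive statistics to characterize the study participants and survey data".
- Continuous secondary outcomes: "To assess whether there was a significant improvement in the continuous secondary cognitive/behavioral outcomes from baseline to end of study", two-sided paired t-tests are planned. If the differences look asymmetric or non-normal, "the non-parametric Wilcoxon signed-rank test will be performed in lieu of paired t-tests".
- Proportions: "We will use the McNemar's test for to compare paired proportions". No outcome is named.

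Table 1 in section 5.0 has three categorical secondary outcomes measured at both T0 and T1: study-specific knowledge items, study-specific attitude items, and readiness for change. The last is described as "Four items assessment resources to assess stage of change based on the Transtheoretical Model (TTM) of behavior change", and the table adds: "It includes questions on physical activity, medication management, glucose self-monitoring, and diet". The response options, number of stages and scoring are not given.

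Section 5.0 says that pre/post change in the secondary outcomes is assessed "to estimate effect size and standard deviations for power analyses necessary to plan subsequent randomized controlled trials". On size it says: "Our target enrollment is 65 participants". Section 6.0 names the System Usability Scale (SUS) score at T1 as the primary outcome.

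**The concern.** Stage of change suggests more than two ordered levels. McNemar's test works on a two-by-two table, and the t-test and Wilcoxon test are tied to continuous outcomes. If McNemar's test is the only route left, each item must be split in two, and the plan does not say where.

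Three things would then be at stake. A move that does not cross the split is not counted. The effect size, which is meant to help plan later trials, would depend on the split. And a split chosen after looking at the data would raise the chance of a false positive finding.

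**Working it through.** The plan gives no power, alpha or effect figure for these items, so there is nothing to reproduce. The check has two parts: how much the cut could matter, and whether the text requires a cut at all.

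**Inputs.** From the documents: 65 participants, four categorical items, T0 and T1. Assumed, because the documents are silent: five stages (three in one case); each person moves up one stage with probability 0.25 and down one with probability 0.05, never beyond the ends of the scale; no moves of two or more stages; 65 complete pairs; two-sided alpha 0.05.

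**Net shift at one cut.** With p(k) the baseline share at stage k, the net shift across the cut between k and k+1 is 0.25 × p(k) − 0.05 × p(k+1). For the uniform baseline, 0.25 × 0.20 − 0.05 × 0.20 = 0.040 at every cut. For the clustered baseline at the third cut, 0.25 × 0.55 − 0.05 × 0.15 = 0.130.

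| Baseline (stages 1 to 5) | Net shift by cut, points | Sum |
|---|---|---|
| Uniform: 0.20 each | 4.0, 4.0, 4.0, 4.0 | 16.0 |
| Spread: 0.10, 0.20, 0.25, 0.20, 0.25 | 1.5, 3.75, 5.25, 3.75 | 14.25 |
| Clustered: 0.05, 0.10, 0.55, 0.15, 0.15 | 0.75, −0.25, 13.0, 3.0 | 16.5 |

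Dependence on the cut is therefore absent, modest or strong according to the assumed baseline. The clustered case alone would overstate it.

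**Comparison with all moves.** Up minus down over all stages, clustered, is 0.25 × (1 − 0.15) − 0.05 × (1 − 0.05) = 0.2125 − 0.0475 = 0.165. That is the sum in the last column. Under one-stage moves each move crosses exactly one cut, so a single cut tends to look small beside the total by construction. A two-stage move would cross two cuts but count once in a sign test.

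**Precision.** The Wald 95% half-width for up minus down, clustered, is 1.96 × √((0.2125 + 0.0475 − 0.165²)/65) = 0.117. For the spread baseline at the third cut, the shares crossing are 0.25 × 0.25 = 0.0625 up and 0.05 × 0.20 = 0.01 down, so the half-width is 1.96 × √((0.0725 − 0.0525²)/65) = 0.064. The range across cuts in that case, 5.25 − 1.5 = 3.75 points, is smaller than 6.4. In the clustered case the range, 13.25 points, exceeds the corresponding third-cut half-width: 1.96 × √((0.1375 + 0.0075 − 0.13²)/65) = 0.087.

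**Power.** Exact enumeration, McNemar's test at the third cut (the upper cut with three stages) against an exact sign test on all moves:

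| Baseline | McNemar | Sign test |
|---|---|---|
| Spread | 13.5% | 60.8% |
| Uniform | 6.2% | 72.0% |
| Clustered | 78.6% | 71.1% |
| Three stages (0.2, 0.5, 0.3) | 58.6% | 58.8% |
| Ceiling (0.05, 0.10, 0.10, 0.15, 0.60) | 0.4% | 11.3% |

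The sign test often does better, but it can tie or lose, and both tests are weak with a ceiling. They also answer different questions: crossing a threshold, or moving at all.

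**Does the text require a cut?** Section 6.0 ties McNemar's test to no outcome. The knowledge items in Table 1 could plausibly be scored right or wrong, and attitude items could be binary; either would give that sentence a use. The descriptive sentence covers survey data, which include the readiness items. What the text supports is that no inferential method is assigned to them, not that they must be collapsed.

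**The case for a change.** The strongest case for acting is that section 5.0 commits to assessing pre/post change in every listed secondary outcome and gives a purpose for it, so the effect measure ought to be defined. The Wilcoxon test is worded for continuous outcomes only, and separate T0 and T1 distributions do not show who moved.

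A late choice of cut also has a price. In a simulation of 3,000 trials per setting (65 pairs, latent-normal items with equally likely stages at T0, T0–T1 correlation 0.6, no true change), taking the best cut gave exact McNemar p ≤ 0.05 in 5.8% of trials with three stages, 8.0% with four and 9.3% with five. A single fixed cut gave 2–3%. With a latent shift of 0.3 SD, a signed-rank test on the ordered stages had 56%, 62% and 63% power, against 27–33%, 23–32% and 19–33% for McNemar's test at single cuts.

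What stands is that coding and paired method are unstated, and that an ordered analysis often has more power. It does not follow that the plan commits to the weaker one. The inflated error arises only if someone collapses the item and then shops for a cut. No single replacement is clearly best: signed-rank, marginal homogeneity, a sign test or one fixed cut would each serve. The sign test ignores the size of a move. The signed-rank test uses it and is already in the SAP.

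**Conclusion.** No change to the plan. This is missing detail that an analyst would fill sensibly: look at the response options, cross-tabulate T0 by T1, and use McNemar's test where an item is binary or a paired method for ordered data where it is not. The T0-by-T1 tables need no data beyond the two planned questionnaires.

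The consequence is small. Readiness is one of three categorical secondary outcomes in a one-month, single-group usability study. The comparison of mean SUS with 71 does not depend on it. The standard deviations wanted for later trials come from the continuous scales, which make up most of the secondary list, and an up-minus-down figure from one group is only a partial input for planning a two-arm trial.

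Every number on dependence on the cut rests on assumed stage counts, baselines and movement rates. The documents cannot say which case applies, and the assumptions range from no dependence (4.0 points at every cut) to strong dependence (−0.25 to 13.0). The conclusion would be different if the SAP had assigned McNemar's test to these items, or if they carried a primary claim; neither is so.
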